12.1 Sample size determination

Sample size calculation was made for the primary objective only. We assess potential differences between the predictive performances of the two models (1) and (2), while maintaining ethical and economic considerations. We consider the positive likelihood ratio (positive LR) as a performance measure, which is defined by a ratio of sensitivity to 1-specificity. A higher positive LR means greater predictive information of positive test results irrespective of disease prevalence. Based on preliminary data obtained from mpMRI, we assume that the sensitivity and specificity of model (1) are both given by 0.789. For model (2), we assume conservatively that the sensitivity will be increased by 0.02 (2%) and that the specificity would improve by 0.15 (15%). In this scenario, the positive LR of model (1) is given by 3.74 and the positive LR of model (2) is calculated as 5.02. In order to detect the 1.28 difference in positive LR between the two models, we need at least 100 subjects, including at least 38 of 100 subjects with a histological diagnosis of significant PCa. The sample size was estimated as described in the literature.⁵⁸

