7.2 Inclusion criteria

Male subjects (≥ 18 years of age) with prior mpMRI (within 3 months of recruitment) resulting in at least one PI-RADS 3-5 lesion with clinical need for a prostate biopsy procedure can participate, if one of the 2 criteria apply:

- Known Gleason 6 (3+3) or 7 (3+4, 4+3) prostate cancer undergoing active surveillance or in the confirmation phase of active surveillance,
- or
- Rising PSA with either a) no prior biopsy or b) single or multiple negative prior biopsies.

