12 STATISTICAL EVALUATION

Accrual potential: At the University of Michigan, over 800 patients receive a prostate biopsy per year (812 in 2016, 652 in 2015, 444 in 2014). The number of navigated TRUS-MRI fusion (targeted) prostate biopsies is rapidly increasing and reached 310 in 2016. In 2016, the Department of Radiology performed 960 mpMRI studies, of which about 60% (576) had a PI-RADS score ≥ 3 .

Prevalence of significant PCa: Among all patients with PI-RADS score ≥ 3 , the incidence of Gleason $\geq 3+4$ PCa is 15% for PI-RADS 3, 55% PI-RADS 4, and 80% PI-RADS 5. At our center, the sensitivity/specificity for Gleason $\geq 3+4$ is 96.5/59.7% for PI-RADS ≥ 3 , and 78.9/78.9% for PI-RADS ≥ 4 . The patient population for this trial will closely resemble a recently retrospectively investigated surveillance population from 2 centers in the state of Michigan (n=207) of men with clinical stage T1/T2 Gleason 3+3 PCa. The distribution of PI-RADS grading was as follows (unpublished data): PI-RADS 1-2 (37%), PI-RADS 3 (19%), PI-RADS 4 (31%), PI-RADS 5 (13%). This incidence of PI-RADS scores ≥ 3 is used in **Table 1** to estimate the incidence of Gleason 3+3 vs. $\geq 3+4$ vs. benign findings in the trial population. Since we will only select patients with prior mpMRI resulting in PI-RADS 3-5, we will be able to select a specific relevant patient population with a sufficient risk for significant disease (defined as Gleason $\geq 3+4$ PCa).

Disease incidence in study population: We estimate the potential impact of molecular imaging in addition to mpMRI for this trial on the basis of our prior ^{18}F -choline PET/MRI trial.¹⁶ Our final (submitted) data included 90 PI-RADS 3-5 lesions in 56 subjects resulting in 30 “positive” (Gleason $\geq 3+4$) and 60 “negative” (Gleason 3+3 or benign). Using a logistic regression model with two predictors—MRI suspicion score and a ^{18}F -choline lesion-to-background ratio of ≥ 1.58 (AUC = 0.95)—strongly favored the combined model over the mpMRI model alone (AUC = 0.83, $p < 0.001$). The selection of all PI-RADS ≥ 4 lesions for the prediction of Gleason $\geq 3+4$ PCa resulted in an excessive number of false-positive ($n = 27$ [FP]) and false-negative ($n=3$ [FN]) cases. When selecting PI-RADS 5 lesions only, 3 FP and 11 FN cases would have resulted, which indicates missing too many significant cancers. The addition of ^{18}F -choline PET to mpMRI resulted in 5 FP and 5 FN cases.

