Compared to the selection of all PI-RADS ≥ 4 lesions (high sensitivity, poor specificity), the combined ^{18}F -choline PET/MRI model resulted in an improvement of the specificity by +38% with only a modest reduction in sensitivity (-10%). Implementation of this rule would have reduced the number of targeted lesions for biopsy by roughly 50% (from 51 to 25), exemplifying the cost-saving potential of a PET/MRI strategy. Given that ^{68}Ga -PSMA and ^{18}F -choline have different molecular targets (^{68}Ga -PSMA has higher specificity for PCa than ^{18}F -choline), and that the ^{18}F -choline trial investigated a high-risk patient population, these ^{18}F -choline results are not directly transferable to the use of ^{68}Ga -PSMA PET/MRI such as is being investigated in this proposal. Furthermore, any future ^{68}Ga -PSMA PET/MRI rule would likely be constructed differently. For sample size estimates in this trial, we therefore project conservatively that the sensitivity of mpMRI would minimally increase (by 2%, mainly from correctly identifying significant cancers rated as PI-RADS 3), while the specificity would increase by only 15%. Given the known superiority of ^{68}Ga -PSMA over ^{18}F -choline, as well as the known increase of PSMA-expression with increasing aggressiveness (Gleason scoring), we have no reason to assume that the performance of ^{68}Ga -PSMA would be inferior to ^{18}F -choline for the identification of significant PCa. As a result, these sample size estimates are quite conservative.

In conclusion, we are confident that the necessary number of subjects can be recruited with sufficient prevalence of significant PCa in this trial. The inclusion criteria will ensure a sufficient potential for positive imaging findings with ^{68}Ga -PSMA PET/CT, and a very high probability of successful targeting with image-guided biopsy.¹⁶

Table 1. Estimated incidence of Gleason 3+3 vs. $\geq 3+4$ vs. benign biopsy results in the trial population

Maximum PI-RADS risk score per subject	Number of subjects (%)	No prostate cancer Benign %	Total maximum grade Gleason = 3+3 %	Total maximum grade Gleason $\geq 3+4$ %
3	30	16 (53%)	10 (33%)	5 (17%)
4	49	9 (27%)	13 (27%)	26 (53%)
5	21	1 (5%)	3 (14%)	17 (81%)
Total (N)	100	26	26	48

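### The mpMRI benchmark of 0.789/0.789 (LR+ 3.74) does not describe the PI-RADS 3-5 men the trial enrols, so the 1.28 criterion rests on a baseline they are not expected to show per subject

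*Combined protocol and SAP*

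**What the plan says.** Section 7.2 admits men whose mpMRI is "resulting in at least one PI-RADS 3-5 lesion with clinical need for a prostate biopsy procedure can participate", subject to its two clinical routes. Section 12 relies on the same restriction: "Since we will only select patients with prior mpMRI resulting in PI-RADS 3-5", the sponsor expects enough significant disease.

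For the centre, Section 12 reports sensitivity/specificity for Gleason ≥3+4 of "96.5/59.7% for PI-RADS" ≥3 and "78.9/78.9% for PI-RADS" ≥4. Section 12.1 carries the second pair into the sample size: "we assume that the sensitivity and specificity of model (1) are both given by 0.789". For the combined model it assumes an extra 0.02 of sensitivity and 0.15 of specificity. It reports LR+ values of 3.74 and 5.02 and sizes the trial at 100 subjects, at least 38 with significant cancer, to detect the difference of 1.28. The Synopsis and Section 5 make a difference of at least 1.28 the primary outcome.

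Table 1 in Section 12 separately estimates biopsy results for the trial population by maximum PI-RADS score per subject.

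**The concern.** The benchmark and the enrolled men appear to be different populations. In a group where every subject has PI-RADS 3-5, the ≥3 cut calls everyone positive: per-subject sensitivity is 100% and specificity 0%. A source showing 59.7% specificity at that cut must therefore, per subject, contain PI-RADS 1-2 men. They are all test-negative at the ≥4 cut, and they supply most of the true negatives behind the 0.789 specificity. The trial leaves them out.

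Section 12.1 favours LR+ because it does not depend on disease prevalence. That property does not help here. Selecting subjects on the comparator test itself changes its sensitivity, specificity and LR+.

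What is at stake is the primary criterion. An absolute LR+ difference depends on the level it starts from: the same gain in sensitivity and specificity moves LR+ less from a low baseline. A threshold set at one baseline may be out of reach, or mean something else, at another.

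**Working it through.** LR+ = sensitivity / (1 − specificity).

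**The plan's own figures**
- Model (1): 0.789 / 0.211 = 3.74. This reproduces.
- Model (2) with the stated gains: (0.789 + 0.02) / (1 − 0.939) = 0.809 / 0.061 = 13.26, not 5.02. A specificity gain of 0.05 gives 0.809 / 0.161 = 5.02. So 5.02, and with it 1.28, does not follow from +0.15. This is a separate error, but it affects how any comparison with 1.28 is read.

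**PI-RADS ≥4 within PI-RADS 3-5**
- Table 1: sensitivity (26 + 17)/48 = 0.896; specificity (16 + 10)/52 = 0.50; LR+ 1.79. Two rows do not add up (PI-RADS 3 sums to 31 against 30, PI-RADS 4 to 48 against 49). Using Section 12's 15/55/80% incidences on 30/49/21 men instead gives 0.907/0.493, again 1.79.
- Centre figures conditioned on ≥3: sensitivity 0.789/0.965 = 0.818; false-positive rate 0.211/0.403 = 0.524; LR+ 1.56.
- Prior choline trial, 30 positive and 60 negative PI-RADS 3-5 lesions, 27 false positives and 3 false negatives at ≥4: 0.90 and 0.55; LR+ 2.00. This is the weakest source. Those counts imply 27 + 27 = 54 selected lesions, while Section 12 later says 51.

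**Gain of +0.02/+0.15 applied as absolute points in enrolled men**

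| Source | LR+ before | LR+ after | Difference | Ratio | Specificity gain needed for 1.28 |
|---|---|---|---|---|---|
| Table 1 | 1.79 | 0.916/0.350 = 2.62 | 0.83 | 1.46 | 0.20 |
| Centre, conditioned | 1.56 | 0.838/0.374 = 2.24 | 0.68 | 1.44 | 0.23 |
| Choline lesions | 2.00 | 0.920/0.300 = 3.07 | 1.07 | 1.53 | 0.17 |

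If the choline count is reconciled to 51 by taking 24 false positives, that row's difference becomes 0.92/0.25 − 0.90/0.40 = 1.43. Taking 24 true positives, it is 0.82/0.30 − 0.80/0.45 = 0.96. The other two rows do not depend on this.

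**Gain read as applying to an unselected population**
- Conditioned on ≥3, +0.15 becomes 0.15/0.403 = +0.37. LR+ after = (0.809/0.965) / (0.061/0.403) = 5.54; difference 5.54 − 1.56 = 3.98, which meets 1.28.
- With the +0.05 that yields 5.02, the same rescaling gives 2.10 − 1.56 = 0.54. Applied as absolute points to Table 1, +0.05 gives 0.24. Both fall short.

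**What 100 subjects deliver for 1.79 vs 2.62**
Delta method on log LR+, 48 with and 52 without significant cancer, two-sided 0.05. Each variance is (1 − sens)/(48 × sens) + spec/(52 × (1 − spec)), giving 0.0217 and 0.0376. The log ratio is ln(2.62/1.79) = 0.379.
- Independent: SE 0.243, z 1.56, power about 0.34.
- Paired, with an assumed correlation of 0.5 between the two log LR+ estimates: SE 0.175, z 2.16, power about 0.58.

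This is power to reject equal LR+, not to show that a threshold is exceeded.

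**The case against.** A reader might infer that the trial is bound to fail its primary outcome even if PET performs exactly as projected. The documents do not support that, for four reasons.

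- **Population of the gain.** Section 12.1 adds +0.15 to the 0.789 baseline, which suggests the same population for both, and on that reading 1.28 is met. Against this, the projection is introduced as "For sample size estimates in this trial, we therefore project conservatively that the sensitivity of mpMRI would minimally increase", which points to the enrolled men. The text leaves it open.
- **Origin of 1.28.** The threshold was not generated by +0.15, so setting 0.83 against 1.28 compares a gain with a target that came from somewhere else. Correcting 5.02 would remove 1.28 altogether. The baseline mismatch would remain.
- **Unit of analysis.** The primary model is lesion-level, Section 12.5.2 reports per subject and per lesion with truth from all cores, and Section 9.2.1 allows PET-positive targets outside PI-RADS 3-5. Counting such sites as mpMRI-negative would raise mpMRI specificity by an amount the documents do not give. So one cannot say that enrolled men could never show 3.74. Nor is the unit of the centre's 59.7% stated; regions scored 1-2 in MRI-positive men could also produce it.
- **Size of the gain and consequence.** In the choline trial, adding PET left 5 false positives and 5 false negatives, an LR+ of 0.833/0.083 = 10.0. A gain of that size would pass easily, although Section 12 says those results do not transfer directly and calls its own projection conservative. The stated null hypothesis concerns the PET coefficient and does not use the 3.74 baseline, and no section defines a negative trial.

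All four points limit the claimed miss. None makes 3.74 the expected per-subject baseline for a PI-RADS 3-5 population, and Table 1, in the same chapter, contradicts it.

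**Conclusion.** The mismatch holds. Per subject, the plan's sources put mpMRI LR+ at the ≥4 cut in PI-RADS 3-5 men at 1.79 (Table 1), 1.56 (conditioned centre figures) or about 2.0 (choline lesions), against the 3.74 used. The 1.28 criterion is therefore anchored to a baseline this population is not expected to show per subject.

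Whether the projected gain reaches 1.28 is conditional. It falls short (about 0.83; 0.68 to 1.07 with the choline counts as stated) if +0.02/+0.15 are absolute gains in enrolled men, which is the more natural reading of Section 12. It is met (about 3.98) if +0.15 refers to an unselected population.

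These figures assume a PI-RADS ≥4 comparator, the cut to which 0.789/0.789 belongs, and a per-subject unit. Section 12 labels model (1) as PI-RADS ≥3; at that cut the per-subject LR+ in this trial is 1.00 by design.

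**What to change.** - In Section 12.1, replace 0.789/0.789 with PI-RADS ≥4 performance among PI-RADS 3-5 subjects (Table 1: about 0.896/0.50, LR+ 1.79), after reconciling that table's row totals.
- State the population and the unit of analysis to which the baseline and the +0.02/+0.15 gain apply.
- Re-derive the success threshold from those inputs, which also disposes of the 5.02 discrepancy. A ratio of LR+ values is preferable (about 1.46 with Table 1): it varies only from 1.44 to 1.53 across the three sources, while the difference runs from 0.68 to 1.07. Carry the new threshold into the Synopsis and Section 5.
- Align the model labels in the primary-objective paragraph of Section 12 with the ≥4 cut.
- Restate what N = 100 delivers, with sidedness, power and the pairing assumption given.
- State in the objective that sensitivity, specificity and LR+ are conditional on PI-RADS ≥3.

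The cost is protocol and SAP wording plus a fresh sample-size justification, with no added patients or procedures. The downside is that the stated baseline, target and power all become less favourable: about 0.34 to 0.58 for 1.79 vs 2.62 under the assumptions shown.

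### The gains stated in section 12.1 give a model (2) positive LR of 13.26, not 5.02, so the 1.28 used as the primary outcome criterion does not follow from its own inputs

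*Combined protocol and SAP*

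**What the plan says.** Section 12.1 takes the positive LR as its performance measure, "which is defined by a ratio of sensitivity to 1-specificity". For mpMRI alone, "we assume that the sensitivity and specificity of model (1) are both given by 0.789". For mpMRI plus PET, "we assume conservatively that the sensitivity will be increased by 0.02 (2%) and that the specificity would improve by 0.15 (15"%). It then reports that "the positive LR of model (1) is given by 3.74 and the positive LR of model (2) is calculated as 5.02".

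The sample size rests on the gap between those two LRs: "In order to detect the 1.28 difference in positive LR between the two models, we need at least 100 subjects", of whom at least 38 must have significant cancer. The method is given only by citation: "The sample size was estimated as described in the literature".

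The specificity assumption also appears in the text of section 12 before Table 1, "while the specificity would increase by only 15"%, and that paragraph ends by saying that "these sample size estimates are quite conservative". The synopsis and section 5 both make an LR advantage of at least 1.28 the primary outcome.

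**The concern.** The two LRs, the gains and the definition all stand in one paragraph, and they do not agree. The printed LR for model (2) is far too low for a specificity of 0.939. The 1.28 is simply 5.02 minus 3.74, so it inherits the discrepancy, and it is then used both as the effect size behind 100 subjects and as the primary outcome criterion.

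A reader cannot tell whether the trial was sized for an LR difference of 1.28 or of 9.52. Nor is it clear whether 1.28 is an expected effect, a minimum worthwhile difference or a slip. While that is open, the claim that the sample size estimates are conservative cannot be checked.

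**Working it through.** **Inputs (section 12.1).** LR = Se/(1 − Sp). Model (1): Se = Sp = 0.789. Model (2): Se + 0.02 = 0.809 and Sp + 0.15 = 0.939.

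**Model (1).** 0.789/(1 − 0.789) = 0.789/0.211 = 3.739. The plan's 3.74 reproduces, which confirms that the definition is applied as written.

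**Model (2).** 0.809/(1 − 0.939) = 0.809/0.061 = 13.262. The plan prints 5.02. The difference from model (1) is 13.262 − 3.739 = 9.523, and 9.52/1.28 = 7.4.

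**Other readings of the gains.** None gives 5.02.

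| Reading | LR, model (2) |
|---|---|
| Both gains relative | 0.80478/0.09265 = 8.69 |
| Sensitivity absolute, specificity relative | 0.809/0.09265 = 8.73 |
| Sensitivity relative, specificity absolute | 0.80478/0.061 = 13.19 |
| False-positive rate cut by 15% | 0.809/(0.211 × 0.85) = 4.51 |
| Section 12's PI-RADS ≥3 baseline (0.965, 0.597) plus the absolute gains | 0.985/0.253 = 3.89 |

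**Working back from 5.02.**

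- With sensitivity 0.809, the specificity must be 1 − 0.809/5.02 = 0.839, a gain of 0.05. Going forward, 0.809/0.161 = 5.025 (5.0248 unrounded, which prints as 5.02).
- With specificity 0.939, the sensitivity would have to be 5.02 × 0.061 = 0.306. With no sensitivity gain at all the LR is still 0.789/0.061 = 12.93. An error in the sensitivity gain therefore cannot explain the figure.
- 1.28 is a difference and not a ratio: 5.02 − 3.74 = 1.28, while 5.02/3.74 = 1.34.

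**Does the choice matter for 100 subjects? (Illustration only.)** Section 12.1 gives no power, sidedness or assumed pairing, so its calculation cannot be reproduced. I assume a Wald test on the log LR ratio at level 0.05, with n1 diseased and n0 non-diseased subjects, one observation each. The plan does not specify this test. With F = 1 − Sp:

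- Independent tests: Var = Σ over both tests of [(1 − Se)/(n1·Se) + Sp/(n0·F)].
- Fully nested errors, the most favourable pairing: Var = (Se2 − Se1)/(n1·Se1·Se2) + (F1 − F2)/(n0·F1·F2).
- Power = Φ(ln(LR2/LR1)/SE − z), with z = 1.96 two-sided or 1.645 one-sided.

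The log ratios are ln(5.025/3.739) = 0.295 and ln(13.262/3.739) = 1.266. The splits are the plan's minimum, 38/62, and the 48/52 expected from Table 1.

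| Two-sided power | SE independent / nested | Independent | Nested | Nested, one-sided |
|---|---|---|---|---|
| 5.02 vs 3.74, 38/62 | 0.397 / 0.157 | 11% | 47% | 60% |
| 5.02 vs 3.74, 48/52 | 0.427 / 0.170 | 10% | 41% | 54% |
| 13.26 vs 3.74, 38/62 | 0.567 / 0.435 | 61% | 83% | 90% |
| 13.26 vs 3.74, 48/52 | 0.615 / 0.474 | 54% | 76% | 85% |

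Each subject has both mpMRI and PET, so independence is only a lower reference. Counting lesions as independent units at the choline trial's 90 per 56 subjects, which is optimistic, divides each SE by √(90/56) = 1.268. Two-sided nested power then becomes 67% and 60% for 5.02 (38/62 and 48/52), and 96% and 92% for 13.26.

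**The case against.** The arithmetic itself has no answer: nothing elsewhere in the documents corrects it, and stating the gain as both 0.15 and 15% rules out a relative reading. The fair objections concern how far it reaches.

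- **A criterion of at least 1.28 is not contradicted by an expected difference of 9.52, which would satisfy it.** This is right as logic. What fails is the derivation of 1.28. Since section 12.1 presents 1.28 only as the gap between two calculated LRs, the criterion has no other support as written.
- **The sample size may really have been based on the 0.15 gain, with 5.02 a reporting slip.** This is possible. Testing an LR of 13.26 against a fixed 3.74, one-sided 0.05, 80% power and prevalence 0.38, needs 99 subjects; the same calculation for 5.02 needs 640. Those settings are assumed and the match may be chance, but nothing here shows that 100 subjects conflict with the 0.15 gain.
- **The power figures rest on an assumed test.** This stands. Section 12 plans a test of the PET coefficient and a comparison of confidence intervals for the LR. The figures show only that the two effect sizes describe very different trials.
- **The conservatism can be judged from the choline data.** This holds in part. Section 12 sets the 15% against a specificity gain of 38% in that trial, although sensitivity there fell by 10% where a 2% rise is projected here. That bears on the assumed gains, not on whether 100 subjects are enough.
- **The unit is given, because section 12.1 counts subjects.** It does, but the primary model in section 12 is fitted to lesions, so the unit assumed in the sizing still needs stating.

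**Conclusion.** The concern holds. On the plan's own definition and inputs, model (2) has a positive LR of 13.26 and exceeds model (1) by 9.52; the printed 5.02 and 1.28 correspond to a specificity gain of 0.05. This conclusion is exact and needs no assumption beyond section 12.1.

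The documents do not show whether the gain or the LR is wrong. The error is not merely clerical, because 1.28 is both the stated basis for 100 subjects and the primary outcome criterion. Whether 100 subjects are enough is not settled: under the assumed per-subject log-LR test, two-sided, 100 subjects give at most 47% power for 5.02 and 61% to 83% for 13.26 at 38/62. It must be fixed before the primary result is interpreted.

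**What to change.** State in section 12.1 which specificity gain was used, then carry it through.

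- **If +0.15:** restate the model (2) LR as 13.26 and the difference as 9.52 in section 12.1. In the synopsis and section 5, either re-derive the 1.28 criterion or justify it separately as a minimum required difference.
- **If +0.05:** correct the 15% in section 12 and in section 12.1. Support the claim that 100 subjects suffice to detect 1.28 with a calculation that is shown, or replace it with the power or detectable difference that 100 subjects give at 38/62 and at Table 1's 48/52.

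In either case, write out in section 12.1 the formula, power, sidedness, unit of analysis (subject or lesion) and assumed pairing.

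The cost is a wording amendment to section 12.1 and either the synopsis and section 5 or the earlier text of section 12. It adds no patients. The price is that the plan may have to state a less favourable power.

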12.2 Significance Level

All statistical tests will use a 0.05 significance level.

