12.5.2 Analysis of Primary Endpoints

PET images will initially be interpreted by a board certified nuclear medicine physician or a board-certified radiologist experienced in reading PET at the time of the imaging study at Michigan Medicine. Upon request, case report forms and coded ⁶⁸Ga-PSMA PET/CT imaging data will be provided to the FDA for review.

Intraprostatic lesions identified by mpMRI as PI-RADS 3-5 will be graded visually on a two-point scale as either positive or negative for elevated ⁶⁸Ga-PSMA uptake relative to prostatic gland uptake (0=Negative or 1=Positive).

Any focal intraprostatic elevated ⁶⁸Ga-PSMA uptake relative to prostatic gland that was not identified by mpMRI (as PI-RADS 3-5) but was targeted at biopsy will also be evaluated visually as either positive or negative (0=Negative or 1= Positive).

All subjects with histopathology correlates will be analyzed for the primary aim. Sensitivity and specificity, positive and negative predictive values, and accuracy (along with the corresponding two-sided 95% confidence intervals) will be determined on a per-subject and per-lesion basis for ⁶⁸Ga-PSMA-11 PET and mpMRI regarding the detection of Gleason \geq 3+4 cancer. Standard reference of truth is histopathology from all individual biopsy cores, targeted and standard cores.

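### The stated size of 100 men, 38 with significant cancer, does not give conventional power for the 1.28 difference in positive LR that section 12.1 says it is needed to detect

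*Combined protocol and SAP*

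**What the plan says.** Section 12.1 defines the positive LR as sensitivity over one minus specificity. For mpMRI alone, "we assume that the sensitivity and specificity of model (1) are both given by 0.789". For the model that adds PET, it raises sensitivity by 0.02 and specificity by 0.15. It then reports that "the positive LR of model (1) is given by 3.74 and the positive LR of model (2) is calculated as 5.02", and concludes: "In order to detect the 1.28 difference in positive LR between the two models, we need at least 100 subjects, including at least 38" with significant cancer on histology. On method it says only this: "The sample size was estimated as described in the literature".

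Section 12.2 sets the error rate: "All statistical tests will use a 0.05 significance level". Section 12.5.2 reports accuracy measures "along with the corresponding two-sided 95% confidence intervals", and section 12 tests the PET coefficient against a two-sided alternative. The synopsis and section 5 make the same 1.28 the primary outcome. Section 12 compares the two models through confidence intervals for the positive LR and describes the sample size estimates as conservative. No target power, sidedness for the sample size, or assumed agreement between the two models is given.

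**The concern.** A positive LR depends heavily on the false-positive rate, which here is estimated from about 62 men. Moving from 3.74 to 5.02 takes only about a five-point drop in that rate. A sample of 100 looked small for a difference of that size, even with both models read in the same men.

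The interpretation of the primary outcome is at stake. If PET/MRI achieved exactly the named gain, the LR comparison would more likely than not be inconclusive. A reader told that the size was sufficient could then take the result as evidence of no gain.

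**Working it through.** **1. The plan's own figures.**
- mpMRI: 0.789 / (1 − 0.789) = 0.789 / 0.211 = 3.74. This reproduces.
- PET/MRI as written: sensitivity 0.789 + 0.02 = 0.809; specificity 0.789 + 0.15 = 0.939; LR = 0.809 / 0.061 = 13.26. The stated 5.02 does not reproduce.
- An LR of 5.02 with sensitivity 0.809 needs a false-positive rate of 0.809 / 5.02 = 0.1612. That is a specificity of 0.839, a gain of 0.05 rather than 0.15.
- 5.02 − 3.74 = 1.28, the stated target.

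**2. Inputs for the power check.** Sensitivities (Se) 0.789 and 0.809; false-positive rates (F) 0.211 and 0.1612; 38 cases and 100 − 38 = 62 non-cases (12.1); alpha 0.05 (12.2), taken as two-sided. The agreement between models is not stated, so I show independent, half-way and fully nested readings.

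**3. Formula.** The effect is d = ln(5.02 / 3.74) = 0.2945 (unrounded 3.7393). With P and Q the joint probabilities that both models call a case, or a non-case, positive:

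Var(d) = [1/Se1 + 1/Se2 − 2P/(Se1·Se2)] / 38 + [1/F1 + 1/F2 − 2Q/(F1·F2)] / 62

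- Independent (P = Se1·Se2, Q = F1·F2): (1.2674 + 1.2361 − 2)/38 + (4.7393 + 6.2052 − 2)/62 = 0.0133 + 0.1443 = 0.1575; SE 0.397.
- Nested (P = 0.789, Q = 0.1612): (1.2674 − 1.2361)/38 + (6.2052 − 4.7393)/62 = 0.0008 + 0.0236 = 0.0245; SE 0.156.
- Half-way: the variance is the mean of the two, 0.0910; SE 0.302.

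Power = Φ(d/SE − 1.96) + Φ(−d/SE − 1.96). The 95% interval for the LR ratio is the estimate multiplied and divided by exp(1.96·SE).

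| Readings | d/SE | Power, 38/62 | Power, 48/52 (Table 1) | Interval factor, 38/62 |
|---|---|---|---|---|
| Independent | 0.742 | 11.5% | 10.6% | 2.18 |
| Half-way | 0.976 | 16.4% | 14.8% | 1.81 |
| Nested | 1.883 | 46.9% | 41.1% | 1.36 |

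The target ratio is 5.02 / 3.74 = 1.34. Even in the nested case, an interval centred on it reaches down to 1.34 / 1.36 = 0.99 and so includes no gain.

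**4. More favourable choices, still for 3.74 against 5.02.**
- One-sided 0.05 at 38/62: 18%, 25% and 59%.
- Lesions as the unit, assuming 90/56 = 1.61 per man as in the earlier choline trial: about 161 lesions. Treated as independent and split 61/100 (38% positive), the nested case gives 67% two-sided and 77% one-sided. With one third positive, as in that trial (54/107), it gives 69% and 79%.
- Treating 3.74 as a known constant: a limit that only just excludes it, which is about 50% power, needs 400 men two-sided or 282 one-sided.
- Paired simulation at 38/62, two-sided (40,000 trials per setting): about 10% for independent readings and 31% to 42% for nested ones, depending on implementation. The asymptotic 47% is therefore generous.

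For scale, 80% power two-sided at 38% prevalence would take about 222 men (nested) to 1,426 (independent).

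**5. The effect that the written inputs imply.** d = ln(13.26 / 3.74) = 1.266. At 38/62 the SEs are 0.567, 0.505 and 0.435, giving power of 61%, 71% and 83%. At 48/52 it is 54%, 63% and 76%.

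**The case against.** The strongest reply is that the 1.28 may itself be the slip. The written specificity gain of 0.15 appears in section 12 as well as in 12.1, and it leads to 13.26. For that effect the formula gives 61% to 83% at 38/62, and simulation runs higher (64% to 97%). This stands, and it limits the point. A reader might infer that 100 men are too few whichever target is kept. The documents do not support that: if the 0.15 is what was meant, the 1.28 sentence falls away and the low figures do not apply.

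A second reply is that the plan promises no particular power, so no stated power is wrong. That is true, and it rules out saying that the trial cannot detect the difference. But a sentence giving the number needed to detect an effect asserts adequacy, and section 12 calls the estimates conservative.

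Third, the unstated agreement matters greatly. Conditional independence is implausible because the second model contains the PI-RADS score, so the lowest power and the 1,426 men should not be read as likely values. The most favourable agreement still falls short.

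Fourth, section 12 also tests the PET coefficient. A reader might infer that this test is underpowered too. It was not assessed, and the documents give no basis for saying so. It does not rescue the LR comparison, which section 5 names as the primary outcome measure.

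**Conclusion.** The point holds in this form: 100 men with 38 cases do not give conventional power for the 1.28 difference that section 12.1 names. Two-sided asymptotic power is about 11.5% to 47% at 38/62 and about 11% to 41% at Table 1's 48/52. No variant tried reaches 80%.

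This rests on a paired normal-theory test of log LR, on a false-positive rate of 0.161 for PET/MRI (inferred from 5.02), and on reading the goal as showing a difference from zero when the true gain is 1.28. If the wording in section 5 is instead a margin to be exceeded, power at a true gain of exactly 1.28 would be only about the one-sided error rate.

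The shortfall belongs to the stated target and should be resolved together with the mismatch between 5.02 and 13.26, as one correction. It does not follow that the trial must enrol more men. The documents do not show how 100 and 38 were derived, and the conclusion does not depend on knowing.

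**What to change.** 1. Reconcile 5.02 and the 1.28 target with the written specificity gain of 0.15, in section 12.1 and wherever the 1.28 is repeated (synopsis, section 5).
2. Remove the statement that 100 subjects with 38 cancers is the size needed to detect a 1.28 difference.
3. In 12.1, give the power of 100 men for the reconciled effect, with sidedness, unit of analysis and assumed agreement between the models.
4. Give the expected 95% interval width for the LR ratio. At 3.74 against 5.02 it is the estimate multiplied and divided by about 1.36 (nested) to 2.2 (independent).
5. State that an interval including no gain will not be read as excluding a gain of 1.28.

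The cost is a rewording and a less favourable statement of what the trial can detect. No change in enrolment is required.
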